Thus, the objective of this national quality improvement project is to develop an adaptive strategy to improve implementation of VA Risk ID to fidelity. Using a sequential multiple assignment randomized trial (SMART) design, two evidence-based implementation strategies will be evaluated: 1) Audit and Feedback (A/F); 2) A/F plus External Facilitation (A/F+EF). We will evaluate these strategies across several domains based on the RE-AIM OUEST mixed methods framework⁹. In addition to focusing on implementation outcomes, such as the impact of these strategies on implementation of VA Risk ID to fidelity, and potential barriers to adopting these strategies, we will also examine the impact of the clinical innovation (i.e., VA Risk ID) on patient-level outcomes. **Primary Aim:** Among sites that do not meet the benchmark for adequate performance (i.e., completion of secondary screening and CSRE for 80% or more of eligible patients) following 6 months of Implementation as Usual (IAU), does the addition of A/F for 10 months significantly improve scores on VA Risk ID performance measures compared to IAU alone? Secondary Aims: 1) Among sites that continue to not meet the benchmark for adequate implementation after 10 months of A/F, does the addition of EF significantly improve scores on VA Risk ID performance measures compared to A/F alone? 2) Among sites that meet the benchmark following A/F alone, is performance maintained following discontinuation of A/F? Outcomes for primary and secondary aims will use clinical performance measures extracted from VA's External Peer Review Program (EPRP) that reflect key practice elements of VA Risk ID: completion of the primary suicide screen, timely completion of the secondary suicide screen and timely completion of the CSRE. Exploratory Aims: 1) Examine the extent to which VA Risk ID is reaching the intended population and compare the characteristics of Veterans reached to all Veterans eligible for screening: 2) Examine contextual factors that may impact the a) implementation of VA Risk ID to fidelity and b) adoption of the implementation interventions. 3) Examine whether Veterans who receive the CSRE are more likely to receive a safety plan than Veterans who screen positive on the primary screen only. **This project directly**

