Several implementation strategies have been employed to support national implementation of VA Risk ID. To date, a multi-faceted approach has been used to support implementation of the three-stage screening and evaluation process. Strategies have included critical information technology enhancements (i.e., new informatics tools and clinical reminder updates), educational webinars, facility champions, weekly technical assistance calls focused on troubleshooting and building a community of practice, support email address, and a fallout report dashboard to help facilities track incomplete secondary screens and CSREs. Despite these efforts, some facilities will face challenges to implementation. *To*

facilitate continuous quality improvement (QI) of VA Risk ID, ongoing evaluation of VA Risk ID and interventions to improve implementation are needed.

Performance measurement is a critical component of evaluation and ongoing QI. A critical element of any QI program is the ability to reliably measure performance. The VA has been a pioneer when it comes to measuring performance as an essential mechanism in improving quality of care¹¹. The External Peer Review Program (EPRP¹²) is the official data source for monitoring facility performance, which is used to prioritize the quality areas needing most attention. Moreover, there is evidence to suggest that facility performance measurement significantly improves overall quality of care across various conditions¹³⁻¹⁴. In preparing for VA Risk ID implementation, several clinical performance measures that map onto the 3-stage screening and evaluation process for those eligible for depression and PTSD screening were developed. These measures provide a standardized way of monitoring implementation of VA Risk ID to fidelity across VHA facilities and include: **sui40** and **sui51**- completion of primary suicide screen as part of depression and PTSD screening, respectively; **sui2**- same day completion of the secondary screen following a positive primary screen; and **csra1**- same day completion of the CSRE following a positive secondary screen.

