C1. Evaluation Framework. RE-AIM QUEST⁹ will provide an overarching framework for testing the impact of the proposed adaptive implementation strategy. RE-AIM QUEST expands RE-AIM by allowing investigators to understand not only whether Reach, Effectiveness, Adoption, Implementation and

Maintenance vary across sites and conditions, but also how and why these variations occur⁹. Moreover, RE-AIM was selected because of its ability to provide an approach to evaluation that focuses both on the impact of the implementation interventions and the impact of the clinical innovation (Table 1).

RE-AIM Domain	Operationalization	Data Sources			
Level of Evaluation: Clinical Innovation					
Reach	The absolute number and representativeness of Veterans that received the primary, secondary screens and CSRE.	Administrative (CDW) Data			
Effectiveness	Whether Veterans who receive the CSRE are more likely to receive a safety plan (SP) compared to Veterans who screen positive on the primary screen only.	Administrative (CDW) data			
Implementation	Percentage of eligible Veterans sampled at each facility who receive the different stages of VA Risk ID as intended; barriers & facilitators to implementation to fidelity.	EPRP measures			
Level of Evaluation	on: Implementation Strategy				
Effectiveness	Effect of A/F intervention on implementation of VA Risk ID to fidelity compared to IAU alone. Effect of A/F + EF intervention on implementation of VA Risk ID to fidelity compared to A/F alone.	EPRP measures			
Adoption	Number of sites randomized to the implementation interventions that participated. Characteristics of participating/non-participating sites and reasons for participating/not participating.	Key Informant (KI) & Debriefing Interviews			
Implementation	mplementation Percent of sampled instances of implementation intervention delivered to fidelity (i.e., met criteria for adherence).				
Maintenance	Maintenance of adequate implementation following removal of A/F; Sustained implementation of VA Risk ID for high performers	EPRP measures			

Table 1. Application of RE-AIM, Level of Evaluation, Operationalization, and Data Sources

^a All domains will be evaluated at Baseline, Post-Intervention Phase I and II except for maintenance, which will be evaluated at postintervention phase I and II

C2. Design. a. Primary and secondary aims (Effectiveness and Maintenance of the implementation

Figure 2. SMART Design and Intervention Phases

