C3. Data Sources. a. VA Risk ID Clinical Performance Measures: Outcomes for primary and secondary aims will include four clinical performance measures extracted from VA's EPRP that reflect key practice elements of VA Risk ID: primary suicide screening (sui40 and sui51), secondary suicide screening (sui 2) and the CSRE (csra1). These four measures are currently in pilot status as they are being validated. EPRP measures are routinely abstracted monthly. VA Risk ID EPRP measures at baseline evaluation (month 6). month 10 of Intervention Phase I and month 10 of Intervention Phase II will be used to evaluate the effectiveness of the implementation strategies (primary and secondary aims). A specific advantage of using EPRP performance measures is that the actual abstraction and collection of data occurs independently from the evaluation team and program office. A data use agreement will be obtained to facilitate the use of EPRP data for this QI project. VA Risk ID EPRP Validation Process: VHA and EPRP contractors develop the data collection instruments (abstraction tools), which are programmed into abstraction software. Data are collected monthly by the abstractors for a random sample of Veterans and the contractor monitors for irregular abstraction patterns. Once final quarterly data are received, question level response patterns and scoring algorithms may be reviewed. Inter-rater reliability (IRR) on the measures will also be reviewed at least once a year. Upon the IRR review, additional edits may be made to the data collection instrument. Once the measure and instrument are considered stable and the data is considered reliable, they can move out of a pilot status. We anticipate that by the start of this project, these measures will be out of pilot status as they will have gone through several rounds of testing and revisions. If we encounter unanticipated and significant challenges to validation of EPRP VA Risk ID measures, we will use the RE-AIM domain of "reach" as our primary outcome measure. **b. Corporate Data Warehouse (CDW):** CDW is a database organized into a collection of data domains derived from the VHA electronic health record. It contains records of inpatient and outpatient care including dates and location of care, as well as associated ICD-10 codes. We will use electronically abstracted data to evaluate reach and effectiveness of the clinical innovation. For Exploratory Aim 1, specific sources of CDW data will include: 1) patient socio-demographic characteristics that allow for comparison between Veterans reached and all Veterans eligible for screening 2) patient responses and results from the screens for Depression, PTSD, and C-SSRS that are administered within Mental Health Assistant; 3) note templates containing the CSRE; and 4) Health Factors recording responses to the CSRE and date of CSRE administration. These sources of data will also serve as data sources for Exploratory Aim 3. Additionally, we will gather health factors specific to the suicide prevention safety plan details and dates. Free-text progress notes may also be abstracted if needed. c. IAU, A/F and EF Debriefing Interviews: Semi-structured interviews will be conducted by an independent evaluator monthly with study team members implementing IAU during the three project phases, A/F during Intervention Phases I and II and EF during Intervention Phase II. The purpose of the interviews is to gather information regarding implementation activities, program and implementation modifications, and implementation barriers and facilitators. The independent evaluator will also use this information to complete the A/F and EF Fidelity Checklists (see below). Draft interview guides are included in Appendix 3. d. Key Informant Interviews: Semi-structured interviews will be conducted with primary care (PC) and primary care mental health integration (PCMHI) leadership and providers after each of the three project phases via telephone. Interviews will explore barriers/facilitators to implementation as well as factors that impact the adoption and utility of the implementation interventions. All interviews will be conducted by the independent evaluator to reduce potential bias. Interviews will be audio recorded and recordings will be transcribed. Draft interview guides for each project phase are included in Appendix 3. e. IAU and EF Activity Logs: A/F and EF Adoption Logs: The IAU Activity Log contains the components of IAU and will be completed monthly throughout each study phase by the independent evaluator. The EF Activity Log²⁴ will be completed by facilitators weekly to track the facilitation activities completed for each site receiving facilitation. The A/F and EF Adoption Logs will be completed weekly by the study team member responsible for sending out A/F and EF communications. These data will be used to determine whether sites adopted the implementation interventions. See Appendix 4 for draft logs. f. A/F and EF Fidelity Checklists: Fidelity checklists will be used to ensure that A/F and EF were delivered as intended.

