
The A/F Fidelity Checklist is based on A/F best practices and will be completed during each month of Intervention Phases I and II by the independent evaluator. To complete the checklist, the evaluator will review a random sample of 25% of sites receiving A/F. If a best practice was not completed, the evaluator will contact the A/F team to inquire why. At the end of Phase II, the evaluator will use information gathered in the qualitative interviews and EF Activity Log to complete the EF checklist, which is based on core IF activities identified through a scoping review and rigorous consensus process²⁷ conducted by QUERI Investigators. Those Investigators plan to pilot a fidelity checklist in early 2019, which will inform the final refinement of our EF Fidelity Checklist. Draft checklists are included in Appendix 5.

C4. Site Selection & Recruitment. a. Site Selection: Up to 140 VAMCs across the country will be recruited to participate in the SMART. Sites will be allocated to various interventions based on performance (i.e., pre-determined benchmarks for adequate implementation- see C6). **b.** Patient Cohort: Although no patients will be recruited for this project, patient level data from EMR will be used for outcomes. The patient cohort of interest for this project are all Veterans eligible for annual depression and as required PTSD screening. **c.** Key Informant Interviews: A purposive sampling approach will be used to recruit up to 20 sites that differ based on geographical location, facility complexity level, and performance level. Interviews will occur at three time points: Baseline, Phase I and II evaluation. Phase I and II evaluations will also include sites who received A/F and A/F + EF, respectively. Up to 6 types of staff/providers from these sites will be invited to participate in the interviews: PC and PCMHI leadership, PC Group Practice Manager, PC Physician, Nursing Staff, and a PCMHI mental health provider.

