EPRP outcomes of change in sui2 and csra1 from the 6th month of the baseline period to the 10th month of the first interventional phase will each be modeled as a function of group (A/F vs. IAU), the baseline outcome value, the stratification variables of facility complexity (high, medium, low) and baseline performance level (above or below the median average fallout rate), and geographic region (West, Midwest, Southwest, Southeast and Northeast). Inference will be made based on the coefficient associated with the group variable and 97.5% confidence intervals (CI) will be reported (alpha=0.025). A similar analysis will be used to determine the effect of A/F on the change in the EPRP outcome for the primary screeners (sui40 and sui51), with 95% CIs reported. **c.** Secondary Aims: 1). To test the effect of the addition of EF for those who do not implement adequately at end of interventional phase 1, the primary EPRP outcomes of change in sui2 and csra1 from the 10th month of interventional phase 1 (baseline for interventional phase 2) to the 10th month of interventional phase 2 will be modeled as a function of group, the baseline outcome value, the stratification variables and geographic region (if sample sizes allow for control of this variable). Inference will be made based on the coefficient associated with the group variable and 95% CIs will be reported. A similar analysis will be used to determine the effect of the addition of EF on the change in the EPRP outcome for the primary screeners (sui40, sui51), with 95% CIs reported. 2). An analysis similar to that described for secondary aim 1 will be employed to investigate the effect of discontinuing A/F for those who implemented adequately at the end of interventional phase 1. Lastly, we will use a data driven approach to characterize each of the four EPRP outcomes over time for each group outlined in Figure 2 (group 1-6). Mixed effects models with a random intercept and slope will be used to model each of the four EPRP outcomes as a function of categorical group (1-6) and an interaction between group and a Bspline transformation on time (allowing the outcome to vary smoothly over time, using 21-time points, i.e., the 6th baseline month and every month of each interventional phase) such that each group will have its own trajectory. The trajectory for each group will be plotted with pointwise confidence intervals. **d. Exploratory** Aims: *i. Reach*: Reach will be calculated using the following formula: actual number of Veterans screened or evaluated/ actual number of Veterans eligible for screening, calculated cumulatively across all three study phases and all sites. We will calculate reach for each assessment stage of VA Risk ID. We will examine representativeness of patients reached by comparing demographic characteristics and other relevant variables (e.g., settings in which screening was completed) between eligible Veterans who were screened and/or evaluated and those who were not. Given that Veterans are clustered within facility, if the intra-class correlation between Veterans within each facility is estimated to be greater than zero, methods appropriate for clustered data will be employed to compare the variables of interest. For continuous variables, linear mixed models will be used with a random facility effect and non-normal data will be transformed. For binary variables, generalized linear mixed models will be used with a logit link and for categorical variables, random effects multinomial models will be employed. If the ICC is zero, t-tests, Wilcoxon rank-sum, Chi-square or Fisher's exact tests will be used, as appropriate. *ii. Adoption & Implementation Factors:* Key informant interviews will be used to examine factors influencing adoption of the implementation interventions and barriers and facilitators of implementing VA Risk ID to fidelity. All qualitative data sources, including interview transcripts and documents will be compiled and managed using Nvivo V. 9.0 software. We will take a general inductive approach³⁴. Specifically, data analysis will be determined by both the research objectives (i.e., domains of the RE-AIM framework) and multiple readings and interpretation of the raw data (i.e., content analysis). The goal is to establish clear links between the research objectives and the summary findings derived from the raw data. *iii. Effectiveness- Clinical Innovation:* We wish to examine whether Veterans who receive the CSRE are more likely to receive a safety plan within 2 weeks than those who screen positive on the primary screen only. To account for clustering of Veterans within facility, a mixed-effects logistic regression will be used to model the outcome of safety plan within 2 weeks (yes/no) as a function of group (receipt of CSRE/positive on primary screen only) with a random subject within facility effect. Additionally, to determine if receipt of a timely safety plan depends on whether Veterans are considered to be at low, moderate or high acute risk of suicide, this model will be repeated with the addition of a group by (categorical) acute risk interaction. Odds ratios for receipt of CSRE relative to positive on primary screen only will be reported for each level of acute risk with 95% confidence intervals.

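### Exploratory Aim 1 uses one reference group for all three stages, so at the secondary screen and the CSRE the representativeness comparison mixes screening positive with being missed

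*Protocol*

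**What the plan says.** Protocol C7.d.i defines reach as "actual number of Veterans screened or evaluated/ actual number of Veterans eligible for screening" and adds: "We will calculate reach for each assessment stage of VA Risk ID". Representativeness is then judged by comparing characteristics "between eligible Veterans who were screened and/or evaluated and those who were not". Table 1 (C1) makes clear that this covers every stage: "The absolute number and representativeness of Veterans that received the primary, secondary screens and CSRE".

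The reference group is the same wherever it is named. Exploratory Aim 1 in the Specific Aims will "compare the characteristics of Veterans reached to all Veterans eligible for screening". C3.b lists as a data source "patient socio-demographic characteristics that allow for comparison between Veterans reached and all Veterans eligible for screening". C4.b sets the cohort: "The patient cohort of interest for this project are all Veterans eligible for annual depression and as required PTSD screening".

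The stages themselves are conditional. In the Background, under performance measurement, sui2 counts secondary screens after a positive primary screen, and csra1 is "same day completion of the CSRE following a positive secondary screen".

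No section gives a stage-specific reference group for reach. The SAP contains no reach or representativeness analysis, so it does not settle the matter.

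**The concern.** Exploratory Aim 1 asks how far VA Risk ID reaches its intended population. That population narrows at each stage by design: a Veteran with a negative primary screen is not due a C-SSRS, and one with a negative C-SSRS is not due a CSRE. If those who received a CSRE are compared with all other eligible Veterans, most of the comparison group was never due one. Any characteristic related to suicide risk will then differ between the groups even when everyone due a CSRE is equally likely to receive it. Conversely, a real shortfall in a higher-risk subgroup is offset, wholly or partly, by that subgroup's higher positive rate.

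At stake is the plan's only planned comparison of which kinds of Veterans are missed, at two of the three stages.

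**Working it through.** The documents give no sample size, power or numeric result for reach, so there is no figure to reproduce. The check decomposes the comparison.

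**Inputs**
- Completion, from C5.a: first-quartile fallout of 47.9% (C-SSRS) and 61.2% (CSRE), so completion c1 = 1 − 0.479 = 0.521 and c2 = 1 − 0.612 = 0.388. Three quarters of sites had higher fallout than this.
- Positivity: **assumed**, because the documents give none. Primary p1 = 2% to 10% of eligible Veterans; secondary p2 = 10% to 50% of those given the C-SSRS.

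**Step 1. What literal reach measures**
- Secondary screen: reach = p1 × c1.
- CSRE: reach = p1 × c1 × p2 × c2.

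**Step 2. Who is in the not-reached group**
- Secondary screen: the share never due it is (1 − p1)/(1 − p1·c1). At p1 = 2%: 0.98/0.98958 = 99.0%. At p1 = 10%: 0.90/0.9479 = 94.9%.
- CSRE: the share due it but missed is p1·c1·p2(1 − c2)/(1 − p1·c1·p2·c2). At p1 = 2%, p2 = 10%: 0.00064, or 0.06%. At p1 = 10%, p2 = 50%: 0.01594/0.98989 = 1.6%.

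**Step 3. Odds ratios for the secondary screen, group B v group A.** The odds ratio between a binary characteristic and being reached is the same whichever is treated as the outcome. Apart from the 52.1%, completion rates in this table are illustrative.

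| Positive A / B | Completion A / B | Literal reach A / B | Literal OR | OR among those due |
|---|---|---|---|---|
| 4% / 4% | 70% / 45% | 2.8% / 1.8% | 0.64 | 0.35 |
| 3% / 6% | 52.1% / 52.1% | 1.6% / 3.1% | 2.03 | 1.00 |
| 4% / 5% | 52.1% / 52.1% | 2.1% / 2.6% | 1.26 | 1.00 |
| 3% / 6% | 70% / 45% | 2.1% / 2.7% | 1.29 | 0.35 |
| 3% / 6% | 80% / 40% | 2.4% / 2.4% | 1.00 | 0.17 |

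For row 4, the literal OR is (0.027/0.973)/(0.021/0.979) = 1.29. Among those due the screen it is (0.45/0.55)/(0.70/0.30) = 0.35.

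The rows show, in order: a real gap diluted; a gap invented; a gap invented under a modest positivity difference; a gap reversed; and a gap hidden. The last needs positivity and completion to cancel exactly, so it is a special case.

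**The case against.** The strongest reply is that the word eligible is not defined by stage in C7.d.i and is used by stage elsewhere. The 80% benchmark, in the Specific Aims and the Figure 2 footnote, refers to eligible patients completing the secondary screen and CSRE, which makes sense only for patients due that stage. On that reading the planned comparison is already the right one. This stands as a genuine ambiguity. It fits the CSRE poorly, however, because C7.d.i divides Veterans evaluated by Veterans eligible for screening, and the Specific Aims and C3.b refer to all Veterans eligible for screening. If the stage-specific meaning was intended, a sentence would settle it.

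Second, the comparison matches the second half of Exploratory Aim 1 as worded. That is so. The plan nowhere states a null hypothesis of equal reach among those due a stage, and should not be faulted for missing one. The criticism is that the named comparator serves the first half of the same aim, reach to the intended population, poorly at the later stages.

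Third, the analysis is exploratory, with no alpha, power or decision rule attached. That also stands and limits the severity.

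A reader might infer three stronger things that the documents do not support:
- *That the later-stage comparison says nothing about who was missed.* With equal positivity a completion gap still shows in the right direction, though diluted (0.64 against 0.35).
- *That a real gap will typically vanish.* Exact cancellation needs particular inputs; dilution or reversal are the other outcomes.
- *That the planned primary and secondary inference is affected.* The Protocol bases it on sui2 and csra1, which are already conditional on the earlier positive screen. C3.a names reach as a fallback primary outcome if those measures cannot be validated, but does not mention the comparison of characteristics.

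**Conclusion.** The point holds on the literal reading, which the Specific Aims and C3.b favour. At the secondary screen and CSRE, one whole-cohort reference group makes the comparison a product of positivity and completion, dominated by who screens positive. The primary-screen comparison is sound.

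The size depends on assumed positivity. At 3% v 6%, the literal odds ratio is 2.03 where the stage-specific one is 1.00, and 1.29 where it is 0.35. With equal completion the false signal roughly follows the ratio of positive rates: 1.26 for 4% v 5%, and 3.06 for 2% v 6%. If a characteristic is unrelated to screening positive, nothing is invented or reversed and only dilution remains.

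Severity is low to moderate: an exploratory analysis, with some ambiguity in the wording, but one whose results could mislead about which Veterans are being missed.

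**What to change.** In C7.d.i, with matching wording in Exploratory Aim 1 and C3.b, define both the reach denominator and the comparison group by stage:

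- **Primary screen:** screened v not screened, among Veterans eligible for annual depression or as-required PTSD screening.
- **Secondary screen:** completed v not completed, among Veterans with a positive primary screen.
- **CSRE:** completed v not completed, among Veterans with a positive secondary screen.

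A comparison of secondary-screen or CSRE recipients with all eligible Veterans can stay as a descriptive yield table, labelled as such and not used to judge reach. The three stages should be read together, because a Veteran missed at the secondary screen does not enter the CSRE denominator.

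The cost is a wording change and a filter in the analysis code. C3.b already lists the depression, PTSD and C-SSRS results and the CSRE records for extraction. The drawback is precision. Under the assumed rates, the secondary-screen comparison would use 2% to 10% of the cohort. The CSRE comparison would use p1 × c1 × p2, from 0.02 × 0.521 × 0.10 = 0.1% to 0.10 × 0.521 × 0.50 = 2.6%. Results at those stages should be given with confidence intervals and their actual group sizes.
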